### 7.5.3 BASELINE AND FOLLOW-UP ASSESSMENTS (WEEK 8, 16, 24)

#### BASELINE ASSESSMENT

After enrollment and app registration, caregiver participants will be sent a link to the baseline survey with questions regarding their vaccine hesitancy, intent to vaccinate, perceived risks and benefits of the vaccine, who they trust for vaccine information, and disease avoidance behaviors. The survey will also ask some household-level questions, including:

- highest education achieved by their children's mother,
- insurance status,
- household members,
- vaccination status of household members,
- COVID-19 infection status of household members,
- increased infection vulnerability status (e.g., chronic health condition or other circumstances increasing vulnerability) of household members, and
- experience of household members with any one of a set of common challenges (e.g., lack of food, housing, etc.).

All these questions, aside from vaccine hesitancy, will come from the RADx-Up Common Data Elements. To assess vaccine hesitancy, caregiver participants will answer questions derived from the WHO SAGE Vaccine Hesitancy Scale that will be adapted to COVID-19 vaccines.

#### **WEEK 8 ASSESSMENT**

**At the week 8 time point**, the caregiver participants will be sent a link to an assessment that asks for the following topics:

1. Vaccine status of eligible children

The surveys will ask caregiver participants for the dates, brands, and administrators for all COVID-19 vaccinations that any of their children received since enrollment, if any. For each vaccinated child, the survey will ask participants to upload a photo of the vaccination card. If a participant is unable to upload the photo or the writing on a card is illegible, the enrolling site personnel will contact the participant to schedule a time for a video conference to view and verify the card information.

2. Usability of the app

Surveys will include a systems usability assessment measured by the System Usability Scale (SUS). The SUS is a simple, ten-item scale giving a global view of subjective assessments of usability. SUS instructions will ask caregiver participants to record their immediate response to each item, rather than thinking about items for a long time. Responses range from Strongly Agree to Strongly Disagree. The SUS yields a single number representing a composite measure of the overall usability of the system. SUS scores have a range of 0 to 100, with 100 representing a perfect score.

#### **WEEK 16 ASSESSMENT**

Caregiver participants will complete an **assessment at or around week 16**. Table 1 lists the content of this assessment.

#### **WEEK 24 ASSESSMENT**

At week 24, participants will be sent a link to an assessment that asks for the vaccine status of eligible children.

#### **PARTICIPANT VACCINE STATUS FOLLOW-UP**

Study staff will assess COVID-19 vaccination status as noted above. For any child who is not card-verified at the 8-, 16-, or 24-week assessment, site coordinators/study team members will review the child's vaccination records in their clinic's electronic medical record system and/or the state immunization registry beginning at Week 25 to determine COVID-19 vaccine status.

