## 7.2 RETENTION

### User Acceptance Pilot Testing

Prior to the start of participant enrollment, the apps for the Vaccine Uptake and General Health app arms will undergo pilot testing to optimize user acceptance. There will be approximately 5 testers from each of the following groups (total: 15):

1. Self-identified rural (English-speaking)
2. Self-identified non-rural (English-speaking)
3. Spanish-speaking

We will ensure that approximately 5 testers among the two English-speaking groups will not be non-Hispanic White. Each testing session will last one hour and will involve reviewing user workflow and formative feedback on app content, including appropriateness of customizations by race, ethnicity, and rurality. User acceptance testing participants will receive \$20 per test in which they participate.

**Participant Remuneration.** Participants in the randomized trial will receive \$20.00 for each assessment that is completed. There are four assessments, these will occur at baseline and weeks 8, 16, 24. The total compensation that participants may receive is \$80.00.

Study team activities to maximize participant retention include the following:

- Enrolling site coordinators will instruct participants to register in the app and will be available to refer participants to the Nebraska App Team if assistance is needed
- Research Team members will contact participants to confirm completion of app registration
- Scheduled push notifications during weeks 1-8 and then monthly for 2 months will prompt participants to engage with in-app content
- *Ad hoc* push notifications regarding national and local updates to vaccine availability/eligibility will prompt participants to engage with in-app content
- Enrolling site coordinators will contact participants at weeks 8, 16, and 24 for follow-up assessments
- Enrolling site coordinators will perform follow-up contact attempts for participants who do not complete their assessments at weeks 8, 16, or 24
- Contact methods for communicating with study participants will comprise multiple modalities, including (but not limited to): email, phone call, and/or text messages

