### 11.4.2 ANALYSIS OF THE PRIMARY EFFICACY ENDPOINT(S)

**COVID-19 Vaccine Series Completion.** For each vaccine-eligible child, the primary endpoint will be whether or not the child initiates and completes the COVID-19 vaccine series during the 24 weeks of the intervention period. The study team will define vaccine series completion as per the current ACIP guidance for the vaccine product. For children who receive a product that requires more than 2 doses for the primary series, receipt of up to 3 doses will be considered complete. Vaccine doses will only be valid for study purposes if given within the 24 weeks of study participation. Additional doses, when required for primary series completion, will only be valid if they are in accordance with ACIP-recommended interval minus a 4-day grace period, in accordance with recommendations of the ACIP. Also, per ACIP, there will be no maximum interval between valid doses. Incorrect second vaccine product (i.e., mixed series) will be invalid for study purposes. The statistical team will use a mixed model with the binomial distribution and the logit link to compare the two intervention groups with respect to the proportions of children who complete COVID-19 vaccination, using a site random effect and controlling for clustering by caregiver.

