4. STUDY ENDPOINTS AND DEFINITIONS

4.1 PRIMARY ENDPOINT

1. Proportion of children who complete COVID-19 vaccination, as verified in state, clinic, or participant-held records

Def: Completion of COVID-19 vaccination will be coded as 1=Yes or 0=No. Verification of vaccine receipt will occur by any of the following methods:

- Photograph of the child's vaccine card, furnished by the caregiver
- Medical records documentation of child vaccine receipt
- Recorded vaccine receipt in the appropriate state vaccine registry

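### The week-25 records check depends on whether a card was verified, not on whether the series was verified complete, so completers whose only card showed a partial series may be missed

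*Protocol*

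**What the plan says.** Protocol 7.5.3 sets out how vaccination status is collected.

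- **Card collection.** The Week 8 Assessment text states: "For each vaccinated child, the survey will ask participants to upload a photo of the vaccination card". If the photo cannot be supplied or read, site staff contact the caregiver to "schedule a time for a video conference to view and verify the card information". Neither step is conditional on the series being complete.
- **Repeat collection.** Table 1 lists child vaccine status at weeks 8, 16 and 24. The Week 24 Assessment text says: "At week 24, participants will be sent a link to an assessment that asks for the vaccine status of eligible children". Section 7.2 adds: "Enrolling site coordinators will contact participants at weeks 8, 16, and 24 for follow-up assessments".
- **Records review.** The trigger is "For any child who is not card-verified at the 8-, 16-, or 24-week assessment". Staff then review the clinic's electronic record and/or the "state immunization registry beginning at Week 25 to determine COVID-19 vaccine status". The term card-verified is not defined.

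The endpoint asks for more than a card. Protocol 11.4.2 requires series completion, with up to three doses depending on the product, and limits the window: "Vaccine doses will only be valid for study purposes if given within the 24 weeks of study participation". SAP 4.1 says: "Completion of COVID-19 vaccination will be coded as 1=Yes or 0=No". It gives no unknown category, and the SAP has no rule for missing outcomes. Protocol 10.1 and SAP 4.1 accept a card photo, the medical record or the registry as verification. Protocol section 4 excludes self-report.

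**The concern.** The trigger asks whether a card was seen; the endpoint asks whether the series was finished. The two differ for a child who has had one dose and needs more. A legible one-dose card at week 8 can count as verified, and if no later card arrives, nothing in the text sends that child to the registry. A child with no card at all does get a records review. The children exposed are therefore those who have started the series and are closest to the primary endpoint.

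The result would be an under-count of completers. The size of the loss depends on caregivers showing updated cards. The trial is unmasked (SAP 3.2.2) and one app is about vaccination, so that behaviour could differ by arm. The documents give neither a rate nor a direction.

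**Working it through.** **Step 1. Does another provision catch the partial-card child?**

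- *Weeks 16 and 24 surveys (7.5.3, Table 1):* yes, if the caregiver responds and shows an updated card. A report of a further dose without a card does not count towards the endpoint (section 4).
- *Lost to follow-up (9.2):* no. Status confirmed by survey or self-report is enough to avoid being classed as lost, so the child need not be flagged.
- *Accepted sources (10.1, SAP 4.1):* these permit use of records but do not order a search.
- *Data quality re-check (12.1.7.1):* covers a subsample only.
- *Coding (SAP 4.1):* 1 or 0, so a child without verified completion would be coded 0.

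The main exposed group is therefore children whose caregiver showed a partial card at week 8 or 16 and no later card. Doses given between the last card and the end of week 24 add a small residual. Initiation is largely untouched, because a valid first dose on the card already counts.

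**Step 2. The plan's own sample size.** Inputs from Protocol 11.2: 30% vs 40%, two-sided 0.05, power 0.90, 2 children per caregiver, ICC 0.60.

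- Children per arm before clustering: (1.96 + 1.2816)² × (0.30×0.70 + 0.40×0.60) / 0.10² = 472.8.
- Design effect 1 + (2 − 1)×0.60 = 1.6. Caregivers per arm: 472.8 × 1.6 / 2 = 378.3, rounded up to 379 (758 in total), as stated.
- 758 / 0.85 = 891.8, rounded up to 892, or 446 per arm, as stated.

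The sample size is not in error.

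**Step 3. Effect of missed completers.** Let L0 and L1 be the shares of true completers missed in the control and app arms. These shares are assumptions. Then p0 = 0.30(1 − L0), p1 = 0.40(1 − L1), and with n caregivers per arm

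power = Φ( (p1 − p0) / √{[p0(1 − p0) + p1(1 − p1)] × 1.6 / (2n)} − 1.96 ).

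Example with L0 = 2%, L1 = 4%, n = 379: p0 = 0.294, p1 = 0.384; variance sum 0.2076 + 0.2365 = 0.4441; standard error √(0.4441 × 1.6 / 758) = 0.0306; 0.090 / 0.0306 = 2.94; Φ(2.94 − 1.96) = 0.84.

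| Assumed loss, control / app | Observed rates | Difference (points) | RR | Power, 379 per arm | Power, 446 per arm |
|---|---|---|---|---|---|
| 0% / 0% | 30% vs 40% | 10 | 1.33 | 90% | 94% |
| 10% / 10% | 27% vs 36% | 9 | 1.33 | 85% | 90% |
| 2% / 4% | 29.4% vs 38.4% | 9 | 1.31 | 84% | 89% |
| 0% / 5% | 30% vs 38% | 8 | 1.27 | 74% | 81% |
| 5% / 0% | 28.5% vs 40% | 11.5 | 1.40 | 96% | 98% |

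In the last row the higher power reflects an inflated effect, not a gain.

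**Step 4. What a given loss would require.** Ignoring the small residual, the loss is roughly (share of completers who sent a partial card) × (share of those who showed no later card). Protocol 2.2 cites retention above 85% in another trial of the same network. If, as an assumption, 15% showed no later card, then a 2% loss needs 0.02 / 0.15 = 13% of completers to have sent a partial card, 5% needs 33%, 10% needs 67%, and 15% needs all of them.

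**The case against.** The strongest reply is that the sentence has a second reading. If a child must be verified at each of the three assessments, one verified at week 8 but not at week 24 goes to review, and almost nothing is lost. The stated purpose, determining vaccine status, fits that reading, and nothing forbids checking records for a child with a partial card. The manual of procedures, which is not among the documents, may settle it. This stands as a limit on how certain the gap is. It does not remove the point: the text does not say which reading applies, and the 15 planned enrolling sites (7.1) could differ.

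The second reply is that follow-up is active. Each assessment pays $20 (7.2), non-respondents get daily reminders for 3 days and then a coordinator contact (9.2), and a video check replaces a missing photo. This also stands, and it keeps the exposed group narrow.

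The third is that the primary population is ITT (11.3), with 892 caregivers to be randomized. At 446 per arm, even a 10% loss in both arms leaves power at the 90% target, and the RR that SAP 6.2 reports does not move. This is correct for equal loss only.

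A reader might go further and infer a large unequal loss, for example 5% of completers in control and 15% in the app arm, which by the same formula gives an RR of 1.19 and power of 45% (379 per arm) or 51% (446). The documents do not support this. They give no rate and no arm difference, and under the assumption in step 4 the 15% would need every app-arm completer to have sent a partial card.

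**Conclusion.** The point holds in a limited form. The records review is not tied to series completion. On the natural reading, a child with a partial card and no later one can be coded a non-completer despite finishing within 24 weeks; on the other reading the gap nearly closes. It would be wrong to infer that the plan rules out records checks for children who have started the series: the wording leaves this open rather than forbidding it.

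The frequency is unknown, so every size given here rests on assumed loss shares. Equal loss is tolerable: RR 1.33 throughout and, at an assumed 10%, 90% power at the planned 446 per arm. Unequal loss matters more, because it biases the RR towards or away from 1 (1.31 at 2% / 4%, 1.27 at 0% / 5%, 1.40 at 5% / 0%). Series initiation is largely unaffected and the planned sample size need not change. The correction is worth making because it concerns the primary endpoint and costs little.

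**What to change.** Replace the trigger in Protocol 7.5.3 with:

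*For every child not card-verified as series-complete through the end of week 24, site staff will review the clinic EMR and the state registry from week 25, counting doses dated within the 24 weeks.*

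State that the rule applies identically in both arms. This resolves the two readings, covers a caregiver who reports a further dose without a new card, and covers doses given after the last card was shown.

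The cost is one sentence plus additional look-ups for children with partial cards. Clinics must already be able to access their state's registry (Protocol 6.1.2), and a review from week 25 is already planned.

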### 6.1.2 SITES

Participating clinics must meet all the inclusion criteria:

- Provide primary pediatric general healthcare to at least 100 unique pediatric patients in the last 12 months; this can include family medicine clinics. Given that primary pediatric care in rural settings often occurs in family medicine clinics, including these clinics as potential performance sites will increase the generalizability of the findings
- Have electronic health record (EHR) or billing database infrastructure to identify potential participants by reviewing the medical records of children within the study inclusion criterion of child-age range
- Have ability to access their state's COVID-19 vaccination registry
- Meet at least one of the following diversity, equity, and inclusion criteria for the patient population served:
  - <60% non-Hispanic White;
  - >40% from a rural zip code as defined by rural-urban community area (RUCA) code ≥4; or
  - >40% on Medicaid/Medicare or uninsured.
- Sites are encouraged, but not required, to have a high Spanish-speaking population.

Sites are not required to stock and administer pediatric COVID-19 vaccines to serve as enrolling sites.

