## 7.4 INFORMED CONSENT

This research study does not involve more than minimal risk of harm to participants and does not involve procedures for which written consent is normally required outside of the research context. The research study has been designed to perform all the study related procedures remotely, and study personnel will not interact in person with potential participants during the intervention. The potential participants will be provided with a written statement regarding the research (ICF+HIPAA) before the consent process. A waiver of consent documentation has been granted for adult participants (parents/caregivers).

Moreover, a full waiver of assent has been requested/granted. Children will not have to sign an assent and/or verbally agree to be part of this study. The ethical justification for requesting a waiver of assent is that this research study does not involve more than minimal risk of harm to participants and does not involve procedures for which written consent is normally required outside of the research context. Children participating in the study involves only medical chart review or access to the state registry to collect COVID-19 vaccination record.

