- **Vaccine access:** Using this pathway, the app will give participants local vaccine availability, recommendations for vaccination (e.g., at what age children can receive the vaccine locally), links to sign-up for a vaccination appointment locally, and resources for traveling to vaccination sites, etc.
- **Push notifications:** The app will deliver messages directly to participants' mobile devices through 8 weekly and 2 monthly push notifications. These messages will direct participants to view specific app content (scheduled once weekly and once monthly, see Table 2 for topic schedule) and alert participants to local or national changes to vaccine availability or vaccination recommendations (as necessary, up to once weekly).
- **Content areas:** The study team will use the Health Belief Model (Section 2.3, Figure 3) to derive general content, and the qualitative study interviews will guide specific content, including (among others identified):
  - Vaccine Safety
  - Vaccine Effectiveness
  - Personal/family susceptibility/vulnerability to COVID-19 disease morbidity and mortality
  - Benefits of vaccination (personal, family, community)
  - Trust in government, healthcare systems regarding vaccination; decision-making/autonomy in choosing vaccination for children
  - Vaccination Availability/accessibility

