## 10. STUDY ASSESSMENTS AND PROCEDURES

### 10.1 EFFICACY ASSESSMENTS

The primary endpoint is child initiation and completion of COVID-19 vaccination by the end of week 24 post caregiver randomization. Verification of vaccine receipt will occur by any of the following methods:

1. Photograph of the child's vaccine card, furnished by the caregiver
2. Medical records documentation of child vaccine receipt
3. Recorded vaccine receipt in the appropriate state vaccine registry

**Title:** Improving pediatric COVID-19 vaccine uptake using an mHealth tool: a randomized, controlled trial

**PI:** [name]

**Secondary endpoint #1** is child receipt of  $\geq 1$  dose of the COVID-19 vaccination series by the end of week 24 post caregiver randomization. Verification of vaccine receipt will be the same as for the primary endpoint.

**Secondary endpoint #2** is enrolled caregiver domain scores on the modified SAGE Vaccine Hesitancy Scale adapted for the COVID-19 Vaccine from baseline and the end of week 16 post caregiver randomization. Caregiver participants will complete this survey electronically.

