3.2.2 Masking

Masking is not planned for this study.

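### The final vaccine-status check may rest on the clinic EMR alone, so a child vaccinated outside the clinic can be coded as not vaccinated

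*Protocol*

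**What the plan says.** Vaccine status is sought first from the caregiver. Protocol 7.5.3 (Week 8 Assessment) states: "For each vaccinated child, the survey will ask participants to upload a photo of the vaccination card". If the photo fails or cannot be read, site staff arrange a video call to view the card. Table 1 shows vaccine status collected again at weeks 16 and 24.

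For a child still not card-verified, 7.5.3 (Participant Vaccine Status Follow-Up) has coordinators "review the child's vaccination records in their clinic's electronic medical record system and/or the state immunization registry beginning at Week 25". Other sections use similar either/or wording:

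- Protocol 10.1, repeated in SAP 4.1: "Verification of vaccine receipt will occur by any of the following methods", followed by card photo, medical record and state registry.
- Protocol 7.4, on the child's part in the study: it "involves only medical chart review or access to the state registry to collect COVID-19 vaccination record".
- Protocol 9.2 treats an EMR or registry check as confirming status, so a child checked that way is not lost to follow-up.

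On the clinics, Protocol 6.1.2 requires that they "Have ability to access their state's COVID-19 vaccination registry", but also says: "Sites are not required to stock and administer pediatric COVID-19 vaccines to serve as enrolling sites". SAP 4.1 (the number appears on both the primary and the secondary endpoint headings) codes completion and initiation as yes or no. It has no category for status not established.

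**The concern.** Accepting any one source is sound for establishing a yes: one valid record of the doses is enough. It does not serve for a no. A clinic EMR that shows no dose is weak evidence that none was given, particularly where the clinic does not vaccinate. The plan has no rule for what establishes a no. A negative EMR-only search counts as confirmed status, and the only code left for that child is 0.

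Doses outside the clinic are foreseeable in both arms. The Vaccine Uptake app offers "links to sign-up for a vaccination appointment locally, and resources for traveling to vaccination sites, etc" (Protocol 8.1.3), and no such pathway is listed for the General Health app (8.1.2). SAP 3.2.2 states "Masking is not planned for this study", and nothing standardises which source a coordinator searches, so the choice could vary by site or by arm without any record of it. At stake is ascertainment of the primary endpoint and secondary endpoint 1. Missed doses shrink the risk difference, and if they are missed at different rates in the two arms they also bias the relative risk, which is the SAP's effect measure.

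**Working it through.** **Inputs** (Protocol 11.2, SAP 3.3): completion 30% v 40%, two-sided alpha 0.05, power 0.90, 2 children per caregiver, ICC 0.60, 379 caregivers per arm, 892 randomised. The ITT population is primary (Protocol 11.3), which gives 892/2 = 446 per arm. The miss rate m, the share of truly completed series not found, is **assumed** throughout because the documents give none.

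**Reproducing the plan.** Children per arm, unpooled formula: (1.960 + 1.282)² × (0.30×0.70 + 0.40×0.60) / 0.10² = 472.8. The design effect is 1 + (2 − 1)×0.60 = 1.6. Caregivers per arm: 472.8 × 1.6 / 2 = 378.3, rounded up to 379. The other four ICC rows also match, and 758/0.85 = 891.8, rounded up to 892.

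**Effect of missed doses.** Observed rates are 0.30(1 − m_control) and 0.40(1 − m_app), with no false positives. Effective children per arm: 379×2/1.6 = 473.75, or 446×2/1.6 = 557.5. Power = Φ(difference/SE − 1.96), with SE = √[(p_c(1−p_c) + p_a(1−p_a))/n_eff].

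Example, 10% missed in both arms, 379 per arm: SE = √[(0.27×0.73 + 0.36×0.64)/473.75] = 0.0300; 0.09/0.0300 = 3.00; Φ(1.04) = 0.85.

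| Missed, control | Missed, app | Observed rates | Difference (points) | RR | Power, 379/arm | Power, 446/arm |
|---|---|---|---|---|---|---|
| 0% | 0% | 30.0% v 40.0% | 10.0 | 1.33 | 90% | 94% |
| 5% | 5% | 28.5% v 38.0% | 9.5 | 1.33 | 88% | 92% |
| 10% | 10% | 27.0% v 36.0% | 9.0 | 1.33 | 85% | 90% |
| 20% | 20% | 24.0% v 32.0% | 8.0 | 1.33 | 79% | 85% |
| 5% | 10% | 28.5% v 36.0% | 7.5 | 1.26 | 70% | 77% |
| 10% | 5% | 27.0% v 38.0% | 11.0 | 1.41 | 95% | 98% |

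The higher power in the last row comes from bias and is not a gain. The 446 column assumes that 30% v 40% holds for everyone randomised, including those who never use the app.

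**How large m might be.** If the EMR lacks every outside dose, m is roughly (share not card-verified) × (share of those vaccinated outside the clinic) × (share searched in the EMR only). With 0.2 × 0.2 × 0.5, m = 0.02 and power at 379 per arm is 89%. With 0.5 × 0.5 × 0.5, m = 0.125 and power is 83.5%.

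**The case against.** A reader might infer that outside doses will be missed more often in the Vaccine Uptake arm, because its app sends families elsewhere, and that the trial is therefore biased toward no effect. The documents do not support this. The access pathway speaks of local sites. Table 2 has example notifications offering the vaccine at the family's own clinic, with that clinic's appointment link, and the clinic customisation adds its contact details and vaccination events. Doses given there would plausibly be in its EMR. Protocol 8.1.2 also describes the control app's notifications as prompting vaccination. The direction of any difference between arms is open.

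A reader might also infer that outside doses will be coded 0 as a matter of course. Several things must coincide: no card verified by photo or video, an outside dose, no registry search, and an EMR that lacks the dose. The surveys also ask who gave each dose, so a caregiver who answers has identified the provider before the record review. The documents do not say whether clinic EMRs hold outside doses.

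Three further points have weight. At the ITT size, a 10% equal loss still gives 90% power. The MOP, site procedures and endpoint training (Protocol 12.1.7) may already direct coordinators to the registry, though the re-confirmation in 12.1.7.1 covers only a subsample of caregiver reports. And registry access is required of clinics, whereas coordinators do the review and clinic staff are kept out of research activities (7.1.1).

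These points limit the size and direction of the problem. They do not remove it: neither document requires a registry search before a child is coded 0.

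**Conclusion.** The gap is real and worth closing. A site that follows the plan as written can settle a child's status on a negative EMR search alone, and the SAP then offers no code but 0. The problem is confined to children who are not card-verified, whose registry record was not searched and whose EMR lacks the dose.

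Its size cannot be determined from the documents. Equal loss costs some power and leaves the relative risk unchanged. Unequal loss would move the relative risk below or above 1.33 depending on which arm loses more, and the plan does not provide for recording which source was searched, so an imbalance in searching might go unseen. All of these figures rest on assumed miss rates, the planned 30% v 40% and ICC 0.60. This is an inexpensive improvement to endpoint ascertainment and not evidence that the result will be biased in a given direction.

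**What to change.** **Protocol 7.5.3:** require a state registry search covering the 24-week window for every child who reaches the record review, in both arms, with the EMR as an additional source. That window also contains the 16 weeks that Protocol 11.4.3 and SAP 6.3.1 give for initiation. Record the sources searched and the dates in the EDC. Bring the either/or wording in 7.4 and 9.2 into line.

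**SAP 4.1, both endpoints:** state that a negative EMR search alone does not establish 0. Treat a child with no verified card, no qualifying record in the EMR and no registry search as status not established. Say how such children enter the main analysis, and add a sensitivity analysis coding them 0. Report verification source by arm.

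**Cost:** one extra look-up for each child who would otherwise be searched only in the EMR, an added EDC field, an IRB-approved amendment, and confirmation that the coordinators doing the review can use the registry access required of the clinics.
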